Participants experiencing toxicity including a DLT may be managed with dose modification or discontinuation from treatment. The proposed doses, schedule(s) and PK time points may be reconsidered and amended during the study based on the emerging safety and PK data.

Assessment of late toxicities will also be completed after the DLT observation period of 28 days after C1D1 for all participants. Once a dose level has been declared safe following the post DLT observation window, participants at lower dose levels who have completed the DLT observation period may escalate to the next higher dose level, if criteria outlined in [Section 4.3.2.1](#), Criteria for Intraparticipant Dose Escalation, have been met.

Participants continuing to experience AEs following discontinuation of treatment will continue to be followed at least every 4 weeks until resolution or determination, in the clinical judgment of the investigator, that no further improvement is expected. Participant will continue a 1-month follow-up visit after the last dose for AE and SAE follow-up if necessary. After the 1-month follow-up, participants will be contacted by telephone every 8 weeks (± 7 days) to obtain information on subsequent anticancer treatment, any AEs/SAEs experienced up to 90 days after the last dose, and survival status until the end of the study ([Section 4.4](#)). If the unresolved AE is considered by the investigator as possibly related to or associated with ADA formation, the participant will be asked to return to the clinic for ADA assessment at approximately 3 month intervals (if feasible given the underlying disease) until the AE or its sequelae return to baseline or stabilize at a level acceptable to the investigator and sponsor, until the last follow-up of the AE.

The biomarker studies will be used to help understand the *in vivo* mechanism of action of the agent(s) studied as well as potential mechanisms of resistance. The studies may help in the future development of PF-07209960 as a single agent, or in combination with other compounds, and may provide information on tumor sub-types that may respond to the study intervention.

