6.6.3. Dose Reductions

Following dosing interruption or cycle delay due to toxicity, the PF-07209960 dose may need to be reduced when treatment is resumed.

No specific dose adjustments are recommended for Grade 1/2 treatment-related toxicity. However, participants experiencing recurrent and intolerable Grade 2 toxicity may resume dosing at the next lower dose level based on investigator's medical judgment once recovery to Grade ≤ 1 or baseline is achieved.

Dose reduction of PF-07209960 by 1 dose level (with maximum reduction to dose level -1, 0.3 mg SC, 0.06 mg IV) ([Table 2](#)) will be allowed depending on the type and severity of toxicity encountered. Participants requiring more than 1 dose reduction will be discontinued from the treatment and entered into the follow-up phase, unless otherwise agreed between the investigator and the sponsor. All dose modifications/adjustments must be clearly documented in the participant's source notes and CRF.

Once a dose has been reduced for a given participant, all subsequent cycles should be administered at that reduced dose level, unless further dose reduction is required. Intraparticipant dose re-escalation may be allowed after discussion between the investigator and sponsor. Participant must not experience a Grade 2 or higher adverse event to be eligible for intraparticipant dose re-escalation.

Table 3. Available Dose Reduction Levels From Starting Dose

Dose Level ^a	SC	IV ^b
Starting	CC1	

a. PF-07209960 dose de-escalation below -1 dose level is not allowed.

b. IV infusion over 1 hour (± 10 minutes)

Participants experiencing a DLT may resume dosing at the next lower dose level (if applicable) once adequate recovery is achieved, and in the opinion of the investigator and sponsor, the participant is benefiting from therapy.

For management of immune-related adverse events, please refer to [Appendix 14](#). For all other toxicities, recommended dose reductions for study intervention are described in Table 4.

Table 4. Treatment Dose Modifications for Study Intervention-Related Toxicity

Toxicity	Grade 1	Grade 2	Grade 3	Grade 4

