6.8.5. Study Treatment Exposure

The Safety Analysis Set will be used.

The following will be summarized by treatment dose level and overall, for Part 1 and by expansion cohort for Part 2:

- Number of participants;
- Duration of Treatment (DOT): DOT is defined as the last active dose date minus the first active dose date + 1. DOT will be summarized, as a continuous variable and summary statistics including the mean, median, standard deviation and range will be provided. In addition, a DOT will be summarized as a categorical variable in 3 month intervals, e.g., the frequency of participants with a DOT of 3 months, 6 months, 9 months, etc.;
- Dose modifications are described in the protocol. Dose modifications to study intervention due to AEs include the following (ideally presented in one table):
 - Number (%) of dose interruptions (include both known and unknown dates). Dose interruptions is defined as a planned dosing day with 0 mg total dose administered;
 - Number (%) of dose interruptions related to AEs, defined as “Was the Actual Dose adjusted from planned?” = “ADVERSE EVENT(S)” and “Latest Action Taken with Study Treatment:” = “DRUG INTERRUPTED”;
 - Number (%) of participants with dose reductions. A dose reduction is defined as a day when the actual dose is less than the planned dose at enrollment and the actual dose is greater than 0 mg (i.e., missed doses are not counted as a reduction);
 - Number (%) of dose reductions related to AEs, defined as “Was the Actual Dose adjusted from planned?” = “ADVERSE EVENT(S)” and “Latest Action Taken with Study Treatment:” = “DOSE REDUCED”;
 - Number (%) of participants with a dose increase. A dose increase is defined as a day when the actual dose is greater than the planned dose;

- Number (%) of participants with dose reductions or interruptions for each reason (AE vs insufficient clinical response vs Other);

The following will be summarized for cumulative dose by dose level in Part 1 and expansion cohort in Part 2:

- Summary statistics (mean, median, standard deviation and range) of cumulative dose and cumulative percent of administered dose (compared to planned dose);
- Actual dose intensity (mg/day): Defined as cumulative actual dose received (mg) divided by the number of doses scheduled per protocol during treatment period;
- Ratio of actual dose intensity to planned dose intensity. Where planned dose intensity is defined as a participant's planned starting dose.

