Listings by participant (ordered by dose level): start date and stop date of dosing period within each cycle (including records with 0 mg), total daily dose received for each dosing period, any missed doses with unknown dates (yes/no), number of missed doses with unknown dates, reason for any dosing changes, and cycle number relative to the dosing period.

Listings by participant and cycle (ordered by dose level): cycle length, total planned dose, total actual dose received, percentage of planned dose, dose reduction (yes/no), and dose interruption (yes/no).

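### The SAP's exposure table measures dose reductions and dose intensity against the enrolment dose, so a one-level reduction after permitted intraparticipant escalation is missed and the intensity ratio is inflated

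*SAP*

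**What the plan says.** Protocol 4.1 provides for intraparticipant escalation in Part 1. Once a higher level has been declared safe, "participants at lower dose levels who have completed the DLT observation period may escalate to the next higher dose level", subject to the criteria in Protocol 4.3.2.1. Protocol 6.6.3 allows "Dose reduction of PF-07209960 by 1 dose level" for toxicity, and by default only once: "Participants requiring more than 1 dose reduction will be discontinued from the treatment and entered into the follow-up phase, unless otherwise agreed".

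SAP 6.8.5 then defines the exposure summaries.

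- Participants with reductions: "A dose reduction is defined as a day when the actual dose is less than the planned dose at enrollment". The dose must also be above 0 mg.
- AE-related reductions: a count of reductions taken from two CRF fields, with no reference to the enrolment dose.
- Increases: "A dose increase is defined as a day when the actual dose is greater than the planned dose". Here the SAP does not say which planned dose it means.
- By reason: "Number (%) of participants with dose reductions or interruptions for each reason". No separate definition is given.
- Cumulative percent of administered dose, compared with an unspecified planned dose.
- "Ratio of actual dose intensity to planned dose intensity". Actual intensity is the cumulative dose divided by the number of scheduled doses. Planned intensity is the participant's planned starting dose.

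The by-cycle listing carries a yes/no reduction flag, also without its own definition. SAP 6.9.1 separately tabulates and lists AEs leading to dose modification.

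**The concern.** The SAP's reference point for a reduction stays at enrolment, while the protocol lets a participant's assigned dose rise. The two fit only for participants who never escalate. For those who do, the SAP rule returns no reduction where the protocol recognises one, and the intensity ratio credits the higher doses without raising the denominator.

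The Part 1 primary objective is safety and tolerability at increasing dose levels. A reduction after escalation is direct evidence on whether the higher level was tolerated, and the row meant to count participants with reductions would not show it. A reader could also see one AE-related reduction reported in the same table as zero participants with a reduction, with nothing in the SAP to explain the difference.

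**Working it through.** The documents state no figure on this point, so there is nothing to reproduce. The check applies the SAP's rules to the dosing paths that the protocol allows.

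**Inputs.** One level up (Protocol 4.1). One level down, once by default (Protocol 6.6.3). Exposure definitions (SAP 6.8.5). Cohorts of about 2 to 4 (Protocol 9.2.1). The dose levels are redacted, so the size of a step is an assumption. Protocol 4.3.2 caps cohort-to-cohort steps at half a log (about 3.16-fold), or 100% (2-fold) after a DLT. I use k = 1.5, 2 and 3.16.

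**Reduction count.** Call the enrolment level 0. One step up gives level 1, and one step down gives 1 − 1 = 0. The actual dose equals the enrolment dose and is not less than it, so the participant is not counted. One such participant changes the row from 1/2 = 50%, 1/3 = 33% or 1/4 = 25% to 0%. This assumes that reduction follows the same dose ladder, with no earlier reduction below enrolment and no agreed second reduction.

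**Dose intensity.** Set the starting dose to 1 and take 10 scheduled doses: 4 at the start level, 2 at the next level, then 4 back at the start level. Cumulative dose is 4 + 2k + 4 = 8 + 2k. The SAP ratio is (8 + 2k)/10. If the planned level rises at escalation and stays there, the planned total is 4 + 6k and the ratio is (8 + 2k)/(4 + 6k).

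| k | SAP ratio | Reference updated at escalation |
|---|---|---|
| 1.5 | 11/10 = 110% | 11/13 = 85% |
| 2 | 12/10 = 120% | 12/16 = 75% |
| 3.16 | 14.32/10 = 143% | 14.32/22.96 = 62% |

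If two of the four final doses are missed, the numerator falls to 6 + 2k. The SAP ratio becomes 90%, 100% or 123%, against 69%, 63% or 54%. At k = 2 the SAP ratio is exactly 100% for someone who was reduced and missed two doses.

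**Rows with an unspecified planned dose.** At k = 2 with no missed doses, the cumulative percent is 12/10 = 120% if planned means the starting dose. It is 12/16 = 75% if planned follows escalation only, and 12/12 = 100% if it follows every assigned change, including the reduction. In the increase row, the same participant counts as 1 against the enrolment dose and 0 against the newly assigned level.

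**The case against.** The strongest reply is that the reduction is not lost. Reductions under Protocol 6.6.3 are for toxicity. The AE-related reduction row works from CRF fields and can record them whatever the enrolment dose, and the SAP 6.9.1 tables of AEs leading to dose modification can do the same. That stands, and it limits the point. A reader might infer that reductions after escalation disappear from the report altogether, and the documents do not support that. What remains is that two rows of one table use different definitions. The CRF-based row counts reductions, not participants, so it does not repair the participant count.

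Second, missed doses have their own interruption row, and the cumulative-percent row might show the shortfall. The first part stands. The second depends on which planned dose is meant, and the SAP does not say.

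Third, the numbers are illustrative, Part 1 expects only about 14 to 22 participants, and listings give actual doses, dates and reasons for changes. All true. The criteria in Protocol 4.3.2.1 are not legible in the public copy, so neither the frequency of escalation nor any reporting rule there can be checked. The legible text speaks of the next higher level and does not clearly support several steps, so the point rests on one step.

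Fourth, grouping AEs and laboratory results by initial dose is stated openly in SAP 5.2. A reader might infer that this is an error, or that it biases the MTD or RP2D. Neither follows. It is a declared convention, and Protocol 4.3.6 and the dose level review draw on all available safety data. No legible section plans a summary by dose at onset, but adding one would be an improvement, not a correction.

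**Conclusion.** The point holds for the exposure summaries. For a participant who escalates one level and is then reduced one level, the participant-level reduction row in SAP 6.8.5 gives a wrong count. The by-reason row and the by-cycle flag do too if they use the same definition. The dose-intensity ratio is inflated after escalation: 110% to 143% against 62% to 85% in the history without missed doses, on assumed step sizes. The increase and cumulative-percent rows are ambiguous.

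The effect is confined to Part 1 participants who escalate, and how many will do so is unknown. First-cycle DLTs, the Bayesian dose-escalation model and the Cycle 1 AE tables are untouched, because escalation comes only after the DLT window. No section makes these tables decisive for the RP2D. It is a stated rule that gives a wrong result in a situation the protocol provides for, and it should be corrected in the SAP before the tables are produced.

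**What to change.** In SAP 6.8.5, define one reference dose: the participant's assigned level, starting at the planned enrolment dose, updated at protocol-permitted intraparticipant escalation but not at reduction. Then:

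- Count as a reduction any non-zero dose below that reference, including later cycles still given at the reduced dose, so that the by-cycle flag does not clear.
- Count as an increase only a dose above the highest level previously assigned. Re-escalation after a reduction, which Protocol 6.6.3 may allow, is then not counted as an increase.
- Use the same reference for the participant, by-reason, cumulative-percent and dose-intensity rows and for the by-cycle flag.
- Reconcile the result with the CRF-based AE-reduction row and explain any difference.

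As a supplement, only if escalation occurs, keep the initial-dose tables, add dose at onset to the DLT and SAE listings, and add one Part 1 summary of AEs and laboratory abnormalities after Cycle 1 by dose level at onset. Read it with its limits: escalated participants are selected for having tolerated a lower dose, exposure differs between levels, and late events may stem from earlier doses.

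The cost is SAP wording and, at most, one set of extra tables from dosing and event dates already collected. No dosing rule changes.

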6.8.6. Concomitant Medications and Nondrug Treatments

Prior, concomitant, and further therapies (drug and non-drug treatments) will be coded by the WHO medical dictionary. Listings of prior, concomitant, and further therapies will be provided separately.

6.9. Safety Summaries and Analyses

All safety analyses will be performed on the safety population.

Summaries and analyses of safety parameters will include all participants in the safety analysis set.

AEs, ECGs, BP, heart rate, and safety laboratory data will be reviewed on an ongoing basis during the study to evaluate the safety of participants. Any clinical laboratory, ECG, BP, and PR abnormalities of potential clinical concern will be described. Safety data will be presented in tabular and/or graphical format and summarized descriptively, where appropriate.

Medical history and physical examination, as applicable, collected during the course of the study will be considered source data and will not be required to be reported, unless otherwise noted. However, any untoward findings identified on physical examination conducted during the active collection period will be captured as AEs, if those findings meet the definition of an AE. Demographic data collected at screening will be reported.

6.9.1. Adverse Events

AEs will be graded by the investigator according to the CTCAE version 5.0 and coded using MedDRA, except CRS, which will be graded by ASTCT criteria (Lee et al, 2019). AE data will be reported in tables and listings. Summaries of TEAEs by primary system organ class and preferred terms, toxicity grade, and seriousness and relationship to study treatment will be presented. In addition, summaries of adverse events leading to death, dose modification, dose interruption, and premature withdrawal from study treatment will be tabulated. The number and percentage of participants who experienced any AE, SAE, treatment related AE, and treatment related SAE will be summarized according to worst toxicity grades. The summaries will present AEs for the entire on-treatment period, by cycle for Part 1 (Cycle 1 and Cycles beyond 1), and for the various parts of the study (by dose level for Part 1 and by expansion cohort for Part 2). In the summary table for Part 1, a “Total” column, summarizing data across all dose levels, will be presented. Listings of AEs leading to dose modification, dose interruption, permanent discontinuation of the study treatment, and death will be provided. Listings of DLTs, deaths, and SAEs will also be provided. Death and SAE information will be based on the data captured from the CRF.

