4.3.6. Recommended Phase 2 Dose Definition

The recommended dose for further study (which is normally the same as the RP2D) is the dose chosen for further investigation based on Phase 1 dose escalation study results. If the MTD proves to be clinically feasible for long-term administration in a reasonable number of participants, then this dose usually becomes the RP2D. Further experience with the MTD may result in a RP2D lower than the MTD. During escalation and prior to an MTD being reached, the sponsor may choose to advance a lower dose into expansion. This decision must be made based on safety, PK, PD, and/or efficacy. Furthermore, after reaching the MTD, up to approximately 6-12 participants may be enrolled in the lower doses for the purpose of refining the RP2D based on emerging safety data.

Significant AEs considered to be related to the study intervention or treatment under investigation that occur after the DLT observation period will be reviewed in context of all safety data available. That review may result in re-evaluation of the MTD/RP2D for Part 2 expansion cohort.

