4. ANALYSIS SETS (POPULATIONS FOR ANALYSIS)

Data for all participants will be assessed to determine if participants meet the criteria for inclusion in each analysis population prior to unblinding and releasing the database and classifications will be documented per standard operating procedures.

Table 2. Analysis Sets

Population	Description
Full analysis set	The full analysis set includes all enrolled participants. "Enrolled" means a participant's, or their legally authorized representative's, agreement to participate in a clinical study following completion of the informed consent process. Potential participants who are screened for the purpose of determining eligibility for the study, but do not participate in the study, are not considered enrolled, unless otherwise specified by the protocol.
Safety analysis set	The safety analysis set includes all enrolled participants who receive at least one dose of study intervention. Unless otherwise specified the safety analysis set will be the default analysis set used for all analyses.
Per protocol analysis set (Evaluable for MTD)	The per protocol analysis set includes all enrolled participants who had at least one dose of study treatment and either experienced DLT or do not have major treatment deviations during the DLT observation period. To be DLT evaluable, a participant must have received at least 75% of their planned doses in each cycle for the first two cycles (i.e., ≥ 11 doses received in each of the first two cycles) and has received all scheduled safety assessments during the DLT window.
Modified Intent to Treat (mITT)	The modified intent to treat (mITT) is the analysis population that will follow the ITT principle and include participants receiving at least 1 dose of study medication with baseline assessment and at least 1 post baseline assessment, disease progression, or death before the first tumor assessment. The mITT population may be used for interim analysis and conference presentations when the study is still ongoing.
PK analysis sets	The PK parameter analysis population is defined as all enrolled participants treated who do not have protocol deviations influencing PK assessment, and have sufficient information to estimate at least 1 of the PK parameters of interest.

Population	Description

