5.2.1. Analyses for Binary Endpoints

Binary data will be summarized by number of unique participant incidence and proportion in the analysis set. A 2-sided 95% CI using Clopper-Pearson exact method will be provided if the sample size per cohort permits.

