6.1.2. Adverse Events (AEs)

- Analysis set: Safety analysis set
- Analysis methodology:

AEs will be characterized by type, frequency, severity (as graded by NCI CTCAE version 5.0, except CRS, which will be graded by ASTCT criteria (Lee et al., 2019)) timing, seriousness, and relationship to study therapy. Further description is given in Section 6.9.1. The primary focus will be on TEAEs. TEAEs is defined as any AE that occurs during the on-treatment period, defined in Section 3.5. AEs that occur after the on-treatment period may still be recorded in the clinical database and will be included in the AE listings, but will not be included in the on-treatment emergent AE summaries.

See Section 6.9.1 for details on the specific AE summaries to be provided.

- Missing data: If an AE start or stop date is missing, imputation will be performed according to Section 5.3.1. The imputed dates will be used to determine whether the AE is to be included in the TEAE summary. The missing AE start or stop dates will be listed as is in AE listings. When the CTCAE grade is missing for an AE, the AE will be excluded from the CTCAE grade summary table.

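### Part 1 AE percentages for cycles beyond the first are taken over the whole safety set, so they can be diluted by up to the share of participants who never start Cycle 2

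*SAP*

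**What the plan says.** SAP 6.9.1 promises percentages: "The number and percentage of participants who experienced any AE, SAE" and the treatment-related versions of both, by worst grade. For Part 1 it splits them "by cycle for Part 1 (Cycle 1 and Cycles beyond 1", by dose level and with a Total column. That section names no denominator for the split.

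The denominator is set elsewhere in the SAP:

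- Section 5.2.1: "Binary data will be summarized by number of unique participant incidence and proportion in the analysis set".
- Section 6.1.2, on Part 1 AEs: "Analysis set: Safety analysis set".
- Section 6.9: "All safety analyses will be performed on the safety population", and then "Summaries and analyses of safety parameters will include all participants in the safety analysis set".
- Section 4, Table 2: "The safety analysis set includes all enrolled participants who receive at least one dose of study intervention".

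Nothing in these sections, or in Protocol 9.4.6.2, limits the later-cycle percentage to participants who reached a later cycle.

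Two further provisions matter. SAP 3.5 runs the on-treatment period to 28 days after the last dose (90 days in an extended version), cut short by new anti-cancer therapy. Protocol 6.1.1 fixes a cycle at 28 days.

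**The concern.** A programmer following these sections would divide later-cycle events by everyone dosed. Those who stop during Cycle 1 have little or no observation time in the later period, so the percentage falls as early drop-out rises, even when the risk among those who continue is unchanged.

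Early exit is also tied to toxicity. Protocol Appendices 14 and 15 list several events that end treatment permanently, so a dose that causes them in Cycle 1 takes its own participants out of later exposure. Participants who are not DLT-evaluable may be replaced (Protocol 4.3.3), but once dosed they stay in the safety set.

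What is at stake is how late toxicity reads across doses. Protocol 4.3.6 reviews significant related AEs that occur after the DLT window and adds: "That review may result in re-evaluation of the MTD/RP2D for Part 2 expansion cohort". Among the planned AE percentage tables, the later-cycle column is the one that separates such events from first-cycle toxicity by dose.

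**Working it through.** The documents give no AE rate, drop-out rate or Cycle 2 entry rate, so there is no plan figure to reproduce. Every value of d, r and q below is an assumption.

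**Notation, per dose level.** N = participants in the safety set. n2 = those dosed in Cycle 2 or later. d = 1 − n2/N. r = proportion of starters with a late AE. q = proportion of non-starters with an AE that is counted in the later period.

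Percentage shown = r(1 − d) + q·d.

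**Step 1: the lower limit, q = 0.** The percentage shown is r(1 − d).

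| r among starters | d = 10% | d = 20% | d = 30% |
|---|---|---|---|
| 30% | 27% | 24% | 21% |
| 50% | 45% | 40% | 35% |

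**Step 2: can q exceed zero?** Yes. Take Cycle 1 as Days 1 to 28, with no new anti-cancer therapy. The on-treatment period of a non-starter then ends at about:

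- Last dose on Day 15: Day 15 + 28 = 43, or 15 + 90 = 105. That is 15 or 77 days past Day 28.
- Day 1 dose only: Day 1 + 28 = 29, or 1 + 90 = 91. That is 1 or 63 days past Day 28.

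The SAP does not say whether an AE in that tail counts as beyond Cycle 1. If it does, the dilution shrinks. With r = 30% and d = 20%, q = 15% gives 0.30 × 0.80 + 0.15 × 0.20 = 27%, and q = 30% gives 30%, which is no dilution. The factor (1 − d) is therefore the largest possible dilution, not its expected size.

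**Step 3: one dose level.** Take N = 6 and 2 starters with a late AE, with q = 0. The SAP rule gives 2/6 = 33.3% (Clopper-Pearson 95% CI 4.3 to 77.7) however many started Cycle 2. Among starters:

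| Started Cycle 2 | Rate among starters | 95% CI |
|---|---|---|
| 6 | 2/6 = 33.3% | 4.3 to 77.7 |
| 5 | 2/5 = 40.0% | 5.3 to 85.3 |
| 4 | 2/4 = 50.0% | 6.8 to 93.2 |
| 3 | 2/3 = 66.7% | 9.4 to 99.2 |

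**Step 4: comparing doses, q = 0.** Two levels of 6 have the same 1-in-3 late risk among starters. If all 6 start at one level and 3 start at the other, the table shows 2/6 = 33.3% and 1/6 = 16.7%. The order can even reverse: r = 30% with d = 10% shows as 27%, while r = 50% with d = 50% shows as 25%.

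**Step 5: the Total column, q = 0.** With 22 treated, 15 starting and 4 with a late AE, the table shows 4/22 = 18.2%, against 4/15 = 26.7% among starters.

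**The case against.** The best case for leaving the plan alone has four parts.

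1. Non-starters are not outside the later period. The 90-day window exists to catch late-onset events, and they can have them. This stands. A reader might infer that someone who stops in Cycle 1 cannot contribute a late event, so that the percentage shown is exactly the starters' rate times the fraction entering Cycle 2. SAP 3.5 does not support that, which is why the figures in Step 1 are limits.

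2. The proportion of all treated participants with an observed late AE is a legitimate summary, and the proportion among those who continue is conditional on a post-treatment event. This stands too. Neither is the one true rate. But the first mixes late risk with early drop-out, so it does not compare late risk between doses.

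3. Decisions do not run through this table. A reader might infer that the MTD is biased. The documents do not support that: Protocol 9.4.1 bases the MTD on first-cycle DLTs in the per-protocol set, Protocol 4.3.6 weighs late AEs against all safety data, and the dose-level review in Protocol 9.6 considers all available study data.

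4. The information can be recovered. SAP 6.8.4 and 6.8.5 tabulate discontinuations and treatment duration and list dosing by participant and cycle. With 14 to 22 participants in Part 1, cases can be read one by one, and the intervals in Step 3 are wide under either denominator. This limits the harm, but it does not make the printed percentage interpretable.

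**Conclusion.** The point holds as one of descriptive reporting. The SAP sections read together set a denominator that includes participants with little or no follow-up in the later period. The later-cycle percentages are diluted whenever non-starters have proportionally fewer counted late AEs than starters, by at most the share not starting Cycle 2. For assumed shares of 10%, 20% and 30%, a 30% rate among starters shows as no lower than 27%, 24% and 21%. If everyone at a dose level starts Cycle 2, there is no dilution. Where early drop-out differs between doses, their percentages are not comparable.

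The problem is confined to the Part 1 by-cycle AE percentages and any intervals on them. Event counts, listings, the entire on-treatment summary, Part 2 (6.9.1 limits the split to Part 1) and the MTD determination are untouched. It is worth correcting before tables are programmed, but it does not threaten the design.

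**What to change.** In SAP 6.9.1:

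- Define the later-cycle denominator as safety-set participants who received at least one dose in Cycle 2 or later. Print that n for each dose level and in the Total column.
- State that AEs with onset after Day 28 in participants who never started Cycle 2 appear in a separate row or listing and remain in the entire on-treatment summary. Without this rule the new denominator would either lose those events or leave them in a numerator whose denominator excludes the participant.
- Keep the safety set for Cycle 1 and for the entire on-treatment period.
- Label the later-cycle percentage as conditional on having continued treatment.

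The cost is a short SAP addition, one extra n and one extra row or listing, from dosing and AE dates already collected. The downside is that the percentage then describes a group selected by continuing. The label makes that plain, and the entire on-treatment table still gives the picture for all treated participants.
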